6.3.2.1. Analysis for Primary Immunogenicity Endpoints

GM level of nAb against the XBB.1.5 strain at Day 15 is the primary endpoint:

The GM level of nAb against the XBB.1.5 strain with corresponding 95% CI will be provided at baseline and Day 15. The 95% CIs will be calculated based on the t-distribution of the log-transformed values then back transformed to the original scale for presentation. The following descriptive statistics will also be provided at baseline and Day 15: the number of participants (n), median, minimum and maximum.

6.3.2.2. Analysis for the Secondary Immunogenicity Endpoints

- The GMR of nAb against XBB.1.5 with 95% CI in the Investigational mRNA-1273.815 treatment group to the licensed Spikevax treatment group at Day 15 will be computed based on the t-distribution of mean difference using the log-transformed values and then back transformed to the original scale for presentation.
- GMFR of nAb against XBB.1.5 with corresponding 95% CI will be provided at Day 15 over baseline level. The GMFR and 95% CIs will be calculated based on the t-distribution of the log-transformed values then back transformed to the original scale for presentation. The following descriptive statistics will be also provided for fold-rise at each timepoint: the number of participants (n), median, minimum, and maximum.
- The number and percentage of participants with seroresponse (SRR) for nAb value against the XBB.1.5 strain at Day 15 will be provided with 95% CI (using Clopper-Pearson method). Seroresponse is defined as nAb value change from baseline (preinjection) below the LLOQ to $\geq 4 \times$ LLOQ, or at least a 4-fold rise if baseline is \geq LLOQ.

In addition, a listing of neutralizing antibodies (nAb) targeting XBB.1.5 and figure for geometric mean levels will be provided, along with a box plot (log scale) illustrating the distribution of nAb levels against XBB.1.5.

6.3.2.3. Immunogenicity Subgroup Analysis

To assess consistency of antibody response across various subgroups, antibody response data will be summarized for each subgroup below. Subgroup analysis for the immunogenicity endpoint will be performed using the same methods described in [Section 6.3.2.1](#) and [Section 6.3.2.2](#).

Immunogenicity will be assessed in the following subgroups:

- Age (≥ 18 to < 65 Years, and ≥ 65 Years)
- Sex (Female, Male)
- Baseline/preinjection SARS-CoV-2 Status (Positive, Negative)
- Race group (White, Black, Asian, Other)
- Ethnicity (Hispanic or Latino, Not Hispanic or Latino)
- Number of prior doses of COVID-19 vaccines (2, 3, 4, ≥ 5)
- Type of prior COVID-19 vaccine (if data warrants)

Subgroups may be combined if necessary.

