9.5. Multiplicity

Multiplicity adjustment is not implemented in this study.

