4.4. Randomization

Approximately 200 adult (≥ 18 years of age) participants will be enrolled and randomized (1:1) to licensed Spikevax or Investigational mRNA-1273.815. Randomization will be stratified by age (18 to < 65 years, and ≥ 65 years).

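### The SAP sets out to assess consistency across subgroups but reports only separate within-subgroup summaries, with no between-subgroup contrast to support a remark on consistency of the product comparison

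*SAP*

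**What the plan says.** SAP 6.3.2.3 states the purpose and then the method: "To assess consistency of antibody response across various subgroups, antibody response data will be summarized for each subgroup below" and "Subgroup analysis for the immunogenicity endpoint will be performed using the same methods described in" SAP 6.3.2.1 and 6.3.2.2. Those sections supply the GM, GMFR and seroresponse rate with 95% CIs by arm, and one treatment contrast: "The GMR of nAb against XBB.1.5 with 95% CI in the Investigational mRNA-1273.815 treatment group to the licensed Spikevax treatment group" at Day 15.

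The factors listed are age, "Sex (Female, Male"), "Baseline/preinjection SARS-CoV-2 Status (Positive, Negative"), "Race group (White, Black, Asian, Other"), ethnicity (two levels) and number of prior COVID-19 vaccine doses (four levels). Type of prior vaccine is optional. The section also allows subgroups to be pooled, without a rule. Age is the stratification factor: "Randomization will be stratified by age (18 to < 65 years, and ≥ 65 years").

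Protocol 9.4.6 lists the subgroups without a method. Protocol 9.2 and SAP 4.2 rule out hypothesis testing, Protocol 4.2 and SAP 4.1 describe the study as descriptive, and Protocol 9.5 says: "Multiplicity adjustment is not implemented in this study". Neither document contains a treatment-by-subgroup term, a ratio of subgroup GMRs, a heterogeneity statistic or a rule for calling subgroups consistent.

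**The concern.** Each subgroup GMR answers whether the two products look alike in that subgroup. Consistency of the product comparison is a different quantity: whether the GMR in one subgroup differs from the GMR in another. On the log scale that is a difference of differences, and its uncertainty is larger than that of either part. It is not among the planned outputs, even for age.

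The study is meant to support a wider lower limit for RNA encapsulation, and a remark that the comparison holds across age or prior infection could become part of that support. With only side-by-side intervals, a reader can go wrong in two ways. One interval that misses 1 may be taken as a real exception when it is chance. A set of intervals that all include 1 may be taken as consistency when the data could not have shown a sizeable difference.

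**Working it through.** The documents give no SD, subgroup prevalence, margin or subgroup error rate, so there is no plan figure to reproduce. Two illustrations follow.

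**Number of levels.** The listed levels are 2 (age) + 2 (sex) + 2 (baseline status) + 4 (race group) + 2 (ethnicity) + 4 (prior doses) = 16. Protocol 5.1 requires at least two primary doses and at least one booster, so the two-dose level should be empty apart from deviations. That leaves 15.

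**Chance patterns when the products are identical.** Taking 15 intervals as independent gives 1 − 0.95^15 = 53.7%. They are not independent, because the same participants recur in every factor, so this was simulated.
- From the plan: 200 participants, 1:1, and a t-based 95% CI for the log GMR in each level.
- Assumed: true GMR of 1 everywhere, factors independent of each other, pooled variance, and no pooling of levels unless stated. A level was skipped if either arm had fewer than two participants.
- Skewed mix A: age 75/25, sex 55/45, baseline status 75/25, race 75/15/5/5, ethnicity 80/20, doses 30/40/30 (%).
- Skewed mix B: 70/30, 50/50, 60/40, 80/12/4/4, 85/15, 20/40/40 (%), in the same order.
- 3,000 trials per layout. The SD cancels out of these rates.

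| Layout | At least one subgroup GMR interval excludes 1 | At least one excludes the overall GMR estimate |
|---|---|---|
| 15 levels, equal prevalences | 41.7% | 17.2% |
| 15 levels, skewed mix A | 41.4% | 22.6% |
| 15 levels, skewed mix B | 39.7% | 20.8% |
| 16 levels, equal prevalences | 44.6% | 19.6% |
| 17 levels (seventh two-level factor added) | 43.9% | 17.6% |
| Five two-level factors (10 levels) | 29.8% | 5.0% |
| Six two-level factors (12 levels) | 31.3% | 4.8% |

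The last column is the closer measure of apparent inconsistency: an interval can exclude 1 without the subgroup differing from the others.

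**Precision of the contrast for age.** With n per arm, a fraction p aged 65 or older, 1:1 allocation within each age stratum and a common SD in log10 units, the 95% interval for the ratio of GMRs is the estimate times or divided by

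10^(1.97 × SD × √(2/(np) + 2/(n(1−p)))).

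Assume n = 95 (the plan randomizes 100 per arm and gives no exclusion rate) and p = 0.25. Then 2/23.75 + 2/71.25 = 0.0842 + 0.0281 = 0.1123, with square root 0.3351, and 1.97 × 0.3351 = 0.660.
- SD 0.4: 10^0.264 = 1.84
- SD 0.5: 10^0.330 = 2.14
- SD 0.6: 10^0.396 = 2.49

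**Best case for a two-level factor.** For a 50/50 split with 100 per arm, the SE of the log ratio is SD × √(2/50 + 2/50) = 0.283 SD. The overall log GMR has SD × √(2/100) = 0.141 SD, so the contrast has twice the SE. At assumed natural-log SDs of 0.8, 1.0 and 1.2, the ratio of GMRs has factors of 1.56, 1.74 and 1.94, against 1.25, 1.32 and 1.40 for the overall GMR.

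**The case against.** The strongest reply is that no error rate exists to be inflated. Nothing is tested, no p-values are planned for subgroups, and no rule says that an interval excluding 1 means inconsistency. A reader might infer from the 40% that the plan produces false subgroup findings in four trials out of ten. The documents do not support that. The figure counts intervals that exclude 1, which is not the same as differing from other subgroups. It also rests on assumed prevalences and falls when levels are pooled, which the SAP permits. This part of the reply stands, as does the point that omitting multiplicity adjustment fits a study without tests.

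A reader might also infer that the uncertainty of a between-subgroup difference is hidden altogether. It is not. The levels of a factor are disjoint, so the log ratio of GMRs is the difference of two reported log GMRs. Its SE is the root of the summed squared SEs, which can be approximated from the two reported intervals and the group sizes. What is missing is the reported contrast, not the information behind it.

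Third, the stated aim is consistency of antibody response, which the GM, GMFR and seroresponse rate by arm and level do describe. The wording permits that reading. The gap concerns consistency of the product comparison, which is what the two-arm design and the per-subgroup GMR invite readers to judge.

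Last, the contrast is itself open to chance. If one interval per factor were read at the 5% level across six factors, independence gives 1 − 0.95^6 = 26.5%. For two factors it is 1 − 0.95^2 = 9.8%. This argues for limiting the addition to two factors and presenting it as an estimate without a test.

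**Conclusion.** The point holds as a modest improvement to a descriptive analysis. The SAP names consistency as the aim, plans no between-subgroup contrast, and so leaves consistency of the product comparison to informal reading. The primary endpoint and the overall GMR are unaffected.

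The chance figures (about 40% for an interval excluding 1 and about 17-23% for one excluding the overall GMR, or about 30% and 5% with five or six two-level factors) show how easily the tables could be misread. They are not operating characteristics of the plan. On precision, with 95 per arm, 25% aged 65 or older and an SD of 0.4-0.6 log10 (all assumed), the age contrast is known only to within a factor of about 1.8 to 2.5 either way. A remark that the age groups are consistent could therefore not exclude roughly a 2-fold difference in GMR.

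**What to change.** In SAP 6.3.2.3 add, for age and baseline SARS-CoV-2 status, the ratio of subgroup GMRs with its 95% CI. Obtain it from a linear model of log10 Day 15 nAb with treatment, subgroup and their product, back-transformed, labelled descriptive and without a test. State that remarks on consistency of the product comparison rest on this interval and not on whether single-subgroup intervals include 1.

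The cost is a few lines of code and one extra column; no new data are needed. The downside is that the interval will be wide, so its main message will be that these subgroup data cannot establish consistency tightly.

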5.1. Inclusion Criteria

Participants are eligible to be included in the study only if all of the following criteria apply:

1. Male or female, at least 18 years of age at the time of consent (Screening Visit) who previously received:
 - a. At least 2 COVID-19 vaccines as primary series (mRNA or non-mRNA or a combination of both) AND
 - b. At least 1 mRNA booster dose (third dose).
2. Capable of giving signed informed consent which includes compliance with the requirements and restrictions listed in the ICF and in the protocol.
3. Participant has provided written and signed informed consent for participation in this study, including all evaluations and procedures as specified in this protocol.
4. Investigator's assessment that participant understands and is willing and physically able to comply with protocol-mandated follow-up, including all procedures.
5. PNCBP may be enrolled in the study. Nonchildbearing potential is defined as surgically sterile (history of bilateral tubal ligation, bilateral oophorectomy, hysterectomy) or postmenopausal (defined as amenorrhea for ≥ 12 consecutive months prior to Screening [Day 0] without an alternative medical cause). A FSH level may be measured at the discretion of the Investigator to confirm postmenopausal status.
6. POCBP may be enrolled in the study if the participant fulfills all of the following criteria:
 - a. Has a negative pregnancy test on the day of injection prior to vaccine dose being administered (Day 1).
 - b. Has practiced adequate contraception or has abstained from all activities that could result in pregnancy for at least 28 days prior to Day 1.
 - c. Has agreed to continue using an effective contraception through 2 weeks following injection.

Note: a list of acceptable contraceptive methods is listed in [Section 10.3](#).

- d. Is not currently breastfeeding.

Adequate female contraception is defined as consistent and correct use of a contraceptive method approved by US FDA ([Section 10.3](#)) or local health agency in accordance with the product label.

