5.2. Exclusion Criteria

Participants who meet any of the following criteria at the Screening Visit (Day 0) or at Day 1, unless noted otherwise, will be excluded from the study:

1. Has known history of SARS-CoV-2 infection within 3 months prior to enrollment.

2. Is acutely ill or febrile (temperature $\geq 38.0^{\circ}\text{C}/[100.4^{\circ}\text{F}]$) less than 72 hours prior to or at the Screening Visit or Day 1. Participants meeting this criterion may be rescheduled and will retain their initially assigned participant number.
3. Currently has symptomatic acute or unstable chronic disease requiring medical or surgical care, to include significant change in therapy or hospitalization for worsening disease, at the discretion of the Investigator.

Clinically unstable is defined as a diagnosis or condition requiring changes in management or medication within the 60 days prior to Screening and includes ongoing workup of an undiagnosed illness that could lead to a new diagnosis or condition.

Asymptomatic conditions and conditions with no evidence of end organ involvement (eg, mild hypertension, dyslipidemia) are not exclusionary, provided that they are being appropriately managed and are clinically stable (ie, unlikely to result in symptomatic illness within the time course of this study). Illnesses or conditions may be exclusionary, even if otherwise stable, due to therapies used to treat them (eg, immunosuppressive treatments), at the discretion of the Investigator.

4. Has a medical, psychiatric, or occupational condition that may pose additional risk as a result of participation, or that could interfere with safety assessments or interpretation of results according to the Investigator's judgment.
5. Reported history of congenital or acquired immunodeficiency (eg, HIV), immunosuppressive condition, asplenia, or recurrent severe infections disease.
6. Has known or suspected allergy or history of anaphylaxis, urticaria, or other significant adverse reaction to the vaccine or its excipients.
7. History of Guillain-Barré syndrome.
8. Has a documented history of myocarditis or pericarditis within 2 months prior to Screening Visit (Day 0).
9. Coagulopathy or bleeding disorder considered a contraindication to IM injection or phlebotomy.
10. Receipt of the following:

- a. COVID-19 vaccine within 3 months prior to enrollment

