6.9. Prior and Concomitant Therapy

6.9.1. Prior Medications and Therapies

Information about prior medications (including any prescription or over-the-counter medications, vaccines, or blood products) taken by the participant within the 28 days before providing informed consent/assent (or as designated in the inclusion/exclusion requirements) will be recorded in the participant's eCRF. All previous COVID-19 vaccinations received prior to informed consent/assent will be recorded.

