9.4.6. Subgroup Analyses

Immunogenicity will be assessed in the following subgroups:

- Age (18 to <65, and ≥ 65 years)
- Sex (female, male)
- Baseline/preinjection SARS-CoV-2 status (negative, positive)
- Race
- Ethnicity
- Number of prior doses of COVID-19 vaccines

Safety may be assessed for the same subgroups.

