6.2.2. Demographics and Baseline Characteristics

Descriptive statistics will be calculated for the following continuous demographic and baseline characteristics: age (years), weight (kg), height (cm), body mass index (BMI) (kg/m^2). The number and percentage of participants will be provided for categorical variables such as age group (18 to <65, and ≥ 65 years), sex (female, male), race and race group (White, Black, Asian, other), ethnicity, baseline SARS-CoV-2 status (positive, negative), number of prior doses of COVID-19 vaccines (2, 3, 4, ≥ 5). Type of prior COVID-19 vaccine may be summarized if data warrants.

The summaries will be presented by treatment group as specified in [Section 6.1](#) based on Safety Set and PPIS.

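### Do the unreachable two-dose level and the undefined vaccine-type subgroup call for a change to the SAP?

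*SAP*

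**What the plan says.** Inclusion criterion 1 (Protocol section 5.1) has two parts that must both be met: "At least 2 COVID-19 vaccines as primary series" and "At least 1 mRNA booster dose (third dose"). Section 5 of the protocol rules out eligibility waivers.

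Protocol section 9.4.6 names the subgroup only as "Number of prior doses of COVID-19 vaccines", without levels. The SAP supplies them twice: as a baseline characteristic in section 6.2.2 ("number of prior doses of COVID-19 vaccines (2, 3, 4", then five or more) and as an immunogenicity subgroup in section 6.3.2.3 ("Number of prior doses of COVID-19 vaccines (2, 3, 4", then five or more). The same subgroup list ends with the type of prior COVID-19 vaccine, to be used if the data support it, and a closing sentence lets subgroups be merged where needed. Section 6.2.2 has a matching optional baseline summary of vaccine type.

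On vaccine history, exclusion 10a (Protocol section 5.2) bars only a "COVID-19 vaccine within 3 months prior to enrollment". Protocol section 6.9.1 states that "All previous COVID-19 vaccinations received prior to informed consent/assent will be recorded". Protocol section 2.2 dates the first XBB.1.5 approvals to September 2023, and the SAP introduction cites protocol amendment 2 of 27 February 2024 and an eCRF of 20 March 2024.

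**The concern.** There are two parts. First, a planned level that no eligible participant can reach suggests that the SAP was not checked against the inclusion criteria; one of the four prior-dose levels would then report nothing.

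Second, the vaccine history that matters most for this endpoint may be a previous dose encoding the same XBB.1.5 antigen. Such a participant could start with a higher titre and have less room to rise. If a difference between the two products is weaker in those participants, the pooled GMR moves toward 1. The trial is meant to support a wider encapsulation limit, so a ratio closer to 1 is the reassuring direction. The GMR in SAP section 6.3.2.2 is unadjusted, randomization is stratified by age alone, and the one subgroup that could show the pattern is conditional and has no stated levels.

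**Working it through.** The plan states no SD, margin, power or expected GMR, so there is no figure of its own to reproduce. The checks are a count, a date comparison, and illustrations on assumed values.

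**1. Minimum prior doses.** Primary series at least 2, plus booster at least 1, gives 2 + 1 = 3. This exceeds the lowest SAP level of 2. In the Per-Protocol Immunogenicity Subset (PPIS), which drops major deviations affecting key data (SAP section 5.4), the two-dose level should be empty or nearly so. In the Safety Set baseline table it could hold a violator who was dosed. SAP section 6.2.1 lists randomized participants with eligibility violations in any case.

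**2. Can someone already given XBB.1.5 enter?** From 30 September 2023 to 27 February 2024 is 31 + 30 + 31 + 31 + 27 = 150 days, longer than the 3-month washout. So yes, it is possible. The documents give neither enrolment dates nor uptake, so the share is unknown.

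**3. How far could the pooled GMR move?** Let r be the GMR in participants without a prior XBB.1.5 dose, f the share with one, and k the fraction of the log-scale effect kept in that share. With f balanced between arms, pooled GMR = r^(1 − f + fk). All inputs are assumptions.

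| r | f | k | exponent | pooled GMR |
|---|---|---|---|---|
| 0.70 | any | 1 | 1 | 0.70 |
| 0.70 | 0.25 | 0.5 | 0.875 | 0.73 |
| 0.70 | 0.50 | 0.5 | 0.75 | 0.77 |
| 0.70 | 0.75 | 0 | 0.25 | 0.91 |
| 0.80 | 0.50 | 0 | 0.50 | 0.89 |

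The range runs from no dilution to substantial dilution, and nothing in the documents places the trial within it.

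**4. Does the seroresponse rate follow the same direction?** Take fold-rise as log-normal, so SRR = Φ[(log10 GMFR − log10 4)/SD], where GMFR is the geometric mean fold-rise. Assume GMFR 15 without and 5 with a prior XBB.1.5 dose, a product effect of 0.70 in the former and half of it on the log scale in the latter.

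- SD 0.45, no prior dose: Φ(1.28) = 90% falls to Φ(0.93) = 82%, a drop of 7.5 points. Prior dose: Φ(0.22) = 59% falls to Φ(0.04) = 52%, a drop of 6.8 points.
- SD 0.35: the drops are 6.5 and 8.7 points respectively.

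A lower SRR lies on a steeper part of the curve, so a product difference need not be harder to see in previously boosted participants.

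**5. What would a committed split show?** The 95% CI factor for a GMR is 10^(t × SD × √(2/n)), with t on 2n − 2 degrees of freedom.

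| log10 SD (assumed) | 100 per arm | 50 per arm |
|---|---|---|
| 0.4 | 1.29 | 1.44 |
| 0.6 | 1.47 | 1.73 |

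If r = 0.70 and half the log effect remains in the other half of the sample, the second GMR is √0.70 = 0.84. The two differ by a factor of 0.84/0.70 = 1.20, which is smaller than the CI factor of either one.

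**The case for a change.** The best argument for acting is that the correction costs almost nothing. The two-dose level is a definite inconsistency, and the merging clause in section 6.3.2.3 deals with sparse cells, not with a level that contradicts eligibility; section 6.2.2 has no such clause. SAP section 6.3.2.3 gives consistency of response across subgroups as its purpose, yet leaves the vaccine-type levels open, so the split could be chosen after unblinding. Type could also be read as mRNA versus non-mRNA, the distinction drawn in criterion 1a ("At least 2 COVID-19 vaccines as primary series (mRNA or non-mRNA or a combination of both) AND"), and prior XBB.1.5 receipt might then never be shown.

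The factual parts stand: the dose levels do not match eligibility, and vaccine type has no stated levels. The consequences are weaker. An empty row alters no estimate at the other levels. Prior XBB.1.5 receipt is not left out of the plan, because the vaccine-type subgroup and its baseline summary can carry it. A firm commitment would also presume that strain is recorded; section 6.9.1 covers all previous COVID-19 vaccinations but does not mention strain, and the eCRF is not among the documents. Dilution is possible, but it would be a feature of the population enrolled. Randomization balances prior XBB.1.5 receipt on average, so the pooled GMR estimates the average effect in that population without bias.

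**Conclusion.** No change follows. The two-dose level is a clerical slip with an expected count of zero among eligible participants; analysts will report an empty row, show a violator, or merge it, and no result or conclusion depends on which. The vaccine-type subgroup is missing detail that analysts can fill sensibly once they see which products were recorded. Baseline geometric means, GMFR and participant listings are planned as well, so differences in starting titre will be visible.

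Making prior XBB.1.5 receipt a mandatory subgroup would be a reasonable preference, but it brings little gain here. There is no hypothesis test or margin (SAP section 4.2), and an even split of 200 participants gives a CI factor of about 1.44 to 1.73 in each half. That range rests on the assumed log10 SD of 0.4 to 0.6 and on the even split; a smaller share on either side would make that side less precise. The dilution figures rest wholly on assumed shares and attenuation, and should not be read as a forecast for this trial.
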